8.2.1.2. Tremelimumab and PF-06801591 Immunogenicity

For patients receiving tremelimumab, the percentage of subjects with positive ADA and neutralizing antibodies will be summarized by dosing cohort. For patients with positive ADA, the magnitude (titer), time of onset, and duration of ADA response (in weeks and months) will also be described, if data permit.

For patients receiving PF-06801591, the percentage of subjects with positive ADA and neutralizing antibodies will be summarized by dosing cohort. For patients with positive ADA, the magnitude (titer), time of onset, and duration of ADA response (in weeks and months) will also be described, if data permit.

Time of onset will be calculated as (date of first positive ADA result - date of first dose of tremelimumab / PF-06801591 + 1). The duration of ADA response will be calculated as (Date of last positive ADA result - date of first positive ADA result + 1). Relevant descriptive statistics (namely mean, median, SD, min, max) maybe summarized for the magnitude (titer), time of onset, and duration of ADA response in weeks and months.

CCI

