18. **Serious and Non-serious Adverse Event Monitoring:** Adverse events should be documented and recorded at each visit using the National Cancer Institute Common Terminology Criteria for Adverse Events (NCI CTC AE) version 5.0. Participants must be followed for AEs for 6 months after the last study treatment administration or until all drug related toxicities have resolved, whichever is later; or earlier than 6 months should the participant commence another anticancer therapy in the meantime. The time period for actively eliciting and collecting AEs and SAEs ("active collection period") for each participant begins from the time the participant provides informed consent through and including 6 months after the last study treatment administration or until all drug related toxicities have resolved, whichever is later. If the participant begins a new anticancer therapy, the period for recording non-serious AEs on the CRF ends at the time the new treatment is started. However, any SAEs occurring during the active collection period must still be reported to Pfizer Safety and recorded on the CRF, irrespective of any intervening treatment.

19. **Concomitant Treatments:** All concomitant medications and non-drug supportive interventions should be recorded in the CRF.

PFIZER CONFIDENTIAL

Schedule of Study Treatment, Pharmacokinetics, Tremelimumab and Sasanlimab Immunogenicity Assessments (Part 1)

Protocol Activity	Screen (£28 days)	Treatment Period												End of Treatment	Post Treatment					
		Cycle 1						Cycle 2							Follow- Up (Months after EOT visit)					
Study Day		Day 1	Day 3 -6	Day 8	Day 15	Day 22	Day 29	Day 43	Day 57	Day 71	Day 85	Day 113			M1	M2	M4	M6		
Cycle Day												Day 1	Day 29	Day 57	Day 85	Day 99		28-35 days		
Visit Window (hours)				±24 hr	±48 hr	±48 hr														
Visit Window (days)							±2	±4	±2	±4	±2	±2	±2	±2	±2	±4		±4	±4	±4
Study Treatment																				
AdC68 ¹ – all participants		X										X								
pDNA ² – all participants							X		X		X		X	X	X					
Tremelimumab ³ – for cohorts assigned to receive tremelimumab		X					X		X		X	X	X	X	X					
Sasanlimab ⁴ – for cohorts assigned to receive sasanlimab		X					X		X		X	X	X	X	X					
Pharmacokinetic s Immunogenicity																				
PK for tremelimumab ⁵		X	X ⁶	X		X		X	X	X		X		X	X					
ADA for tremelimumab ⁵		X						X				X		X			X		X	X
PK for sasanlimab ⁶		X	X ⁸	X		X		X	X	X		X		X	X					
ADA for sasanlimab ⁷		X						X				X		X			X		X	X

PFIZER CONFIDENTIAL

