4. Sasanlimab will be administered subcutaneously in close proximity to the vaccine injected muscle and vaccine draining lymph nodes on Day 1, Day 29, Day 57 and Day 85 of each cycle. During the Maintenance period, sasanlimab will be administered each month. Sasanlimab will be administered after the adenovirus or pDNA and after the tremelimumab.
5. Blood samples for determination of tremelimumab drug concentrations and for detection of ADA/NAb against tremelimumab will be collected as outlined in the [schedule of activities](#). Samples to be collected on dosing days are to be obtained within 6 hours prior to tremelimumab dosing.
6. Blood samples for determination of sasanlimab drug concentrations and for detection of ADA/NAb against sasanlimab will be collected as outlined in the [schedule of activities](#). Samples to be collected on dosing days are to be obtained within 6 hours prior to sasanlimab dosing.

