4.1.2. Part 2 Inclusion Criteria

1. Histological or cytological diagnosis of locally advanced or metastatic NSCLC (squamous or non-squamous histology) meeting the following criteria:
 - a. Receipt of at least 1, but not more than 2, prior treatment regimens in the advanced disease setting. In addition to participants with established metastatic or recurrent disease, the advanced disease setting also includes participants with platinum-based adjuvant, neoadjuvant, or definitive chemoradiation therapy given for locally advanced disease followed by recurrent or metastatic disease within 6 months of completing therapy.

- b. Prior treatment must have included an anti-PD-1/PD-L1 and a platinum-based chemotherapy, which may have been given in combination, or sequentially;
 - c. Prior treatment must have included an appropriate TKI if activating mutations are present, eg, EGFR/ALK/ROS1/BRAF/RET/TRK;
 - d. Most recent treatment must have included anti-PD-1/PD-L1 for at least 4 months, without radiographic disease progression, followed by confirmed radiographic disease progression on or within 12 weeks of the last dose;
 - e. No more than 1 prior anti-PD-1/PD-L1 treatment regimen may have been given;
 - f. Prior anti-PD-1/PD-L1 may not have been discontinued permanently for toxicity.
 - g. No prior treatment may have been given with any immunologic therapy other than anti PD-1 or PD-L1.
2. A mandatory archived formalinfixed paraffin embedded (FFPE) tumor tissue block (preferred) must be provided. If an FFPE tumor tissue block cannot be provided, sites should contact sponsor for approval to submit slides. If an archived FFPE tissue is not available, a de novo (ie, fresh) tumor sample can substitute and should be obtained in accordance with local institutional practice for tumor biopsies.
3. Females and/or male participants age ≥ 18 years.
4. Eastern Cooperative Oncology Group (ECOG) Performance Status (PS) 0 or 1.
5. Measurable disease as per RECIST v. 1.1.
6. Adequate Bone Marrow Function, including:
 - a. Absolute Neutrophil Count (ANC) $\geq 1,500/\text{mm}^3$ or $\geq 1.5 \times 10^9/\text{L}$;
 - b. Platelets $\geq 100,000/\text{mm}^3$ or $\geq 100 \times 10^9/\text{L}$;
 - c. Hemoglobin $\geq 9 \text{ g/dL}$.
7. Adequate Renal Function, including:

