9.1. Analysis Sets

For safety evaluation, participants should have received at least one of the regimen components. For efficacy **CCI** evaluation, participants should have received at least one dose of all components administered on Cycle 1 Day 1. See Section **9.4** for definitions related to efficacy.

Participants who receive the designated investigational product of interest and have at least one post-dose drug concentration measurement will be included in the PK data analysis.

1. Safety analysis set.

The safety analysis set includes all enrolled participants who receive at least one dose of one of the components of the regimen.

2. Full analysis set.

The full analysis set includes all enrolled participants.

3. Per protocol analysis set.

The per protocol (PP) analysis set includes all enrolled participants who receive at least one dose of all regimen components administered on Cycle 1 Day 1 of study medication and who do not have major protocol deviations during the 28 days after the first vaccination.

4. Modified Intention-to-Treat analysis set.

CCI modified Intention-to-Treat (mITT), which is defined as all enrolled participants who received at least one dose of all regimen components administered on Cycle 1 Day 1.

CCI

a participant

must have at least 1 valid and determinate assay result related to the proposed analysis. Participants who have no valid and determinate assay result related to any proposed analysis will be excluded from the mITT analysis set.

CCI

5. PK analysis set.

The PK parameter analysis population is defined as all enrolled participants treated who have sufficient information to estimate at least 1 of the PK parameters of interest and who have no major protocol deviations influencing the PK assessment.

6. Immunogenicity analysis set.

The immunogenicity analysis set includes all enrolled participants who receive at least one dose of the VBIR-2 component that is the subject of the immunogenicity assessment (tremelimumab or sasanlimab).

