9.6.3. Analysis of Immunogenicity Data

The percentage of participants with positive tremelimumab ADA and NAb will be summarized by each cohort. For participants with positive ADA or NAb, the magnitude (titer), time of onset, and duration of ADA or NAb response will also be described, if data permit.

The percentage of participants with positive sasanlimab ADA and NAb will be summarized by cohort. For participants with positive ADA or NAb, and if data permits, the magnitude (titer), time of onset, and duration of ADA or NAb response will be described.

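### ADA incidence, onset and duration do not exclude the pre-dose Day 1 sample, so antibody present before dosing reads as a response with onset of 1 day

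*SAP*

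**What the plan says.** The objective in both parts is the ADA response to tremelimumab and sasanlimab after subcutaneous administration. The matching secondary endpoint is the incidence and titers of ADA and neutralizing antibodies (Protocol 2.1 and 2.2; the SAP repeats the objective in section 2.2).

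- **Incidence, SAP 8.2.1.2:** "the percentage of subjects with positive ADA and neutralizing antibodies will be summarized by dosing cohort", for each of the two antibodies.
- **Onset, SAP 8.2.1.2:** "Time of onset will be calculated as (date of first positive ADA result - date of first dose of" the antibody, plus 1.
- **Duration, SAP 8.2.1.2:** "Date of last positive ADA result - date of first positive ADA result + 1".
- **Incidence, Protocol 9.6.3:** "The percentage of participants with positive tremelimumab ADA and NAb will be summarized by each cohort", with parallel wording for sasanlimab. Titer, onset and duration are to be described if the data permit; no formula is given.
- **Sampling:** the Part 1 and Part 2 treatment and immunogenicity schedules both mark ADA on Day 1. The notes add: "Samples to be collected on dosing days are to be obtained within 6 hours prior to tremelimumab dosing". The sasanlimab note says the same for its own dosing.
- **Analysis set, Protocol 9.1:** "The immunogenicity analysis set includes all enrolled participants who receive at least one dose of the VBIR-2 component" being assessed. SAP 5.5 has the same rule. No ADA sample is required.

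**The concern.** The Day 1 sample is a baseline sample. A positive result there cannot be a response to a drug not yet given, yet nothing legible in the incidence, onset or duration rules sets it aside. Three reported quantities are then affected: the percentage positive includes pre-existing antibody, time of onset is pulled towards Day 1, and duration is counted from before exposure. Neutralizing antibodies have the same gap in their percentage.

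The documents handle baseline explicitly elsewhere. Adverse events are treatment-emergent only if they start or worsen after first dose (Protocol 9.5.1, SAP 6.2.2), and the SAP defines baseline for laboratory tests, vital signs and ECG (6.2.3 to 6.2.5). ADA has no counterpart.

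What is at stake is interpretation. Protocol 1.4.1 attributes the lower antibody exposure seen in monkeys after repeat dosing to ADA. Incidence and onset that mix pre-existing with induced antibody would blur any such link in participants.

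**Working it through.** The plan states no ADA rate, so there is no figure to reproduce. The check applies the SAP formulas to the sampling days.

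**Onset** = first positive day − first dose day + 1.

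- Pre-dose sample on Day 1 positive: 1 − 1 + 1 = 1 day.
- First positive at the next Part 2 ADA visit, Day 29 ± 2: 27 to 31 days. This is the earliest onset the Part 2 schedule can show for an antibody that arises after dosing.

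**Duration** = last positive day − first positive day + 1.

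- Positive from Day 1 to Day 85: 85 − 1 + 1 = 85 days.
- Positive from Day 29 to Day 85: 85 − 29 + 1 = 57 days.

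**Size, on assumed counts.** Take 30 participants (the approximate Part 2 size, Protocol 9.3), 3 emergent cases all first positive on Day 29, and k others positive at baseline. Emergent incidence is 3/30 = 10.0% with mean onset 29 days. As written:

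| k | Incidence, (3 + k)/30 | Mean onset, (3 × 29 + k × 1)/(3 + k) |
|---|---|---|
| 1 | 4/30 = 13.3% | 88/4 = 22.0 days |
| 2 | 5/30 = 16.7% | 89/5 = 17.8 days |
| 3 | 6/30 = 20.0% | 90/6 = 15.0 days |

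The comparison depends on the denominator. Among baseline-negative participants only, 3 cases are 3/29 = 10.3%, 3/28 = 10.7% or 3/27 = 11.1%.

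**When emergent ADA is common.** With 18 emergent cases instead of 3 (60.0%, also an assumption), incidence reads 19/30 = 63.3% to 21/30 = 70.0%. Mean onset reads (18 × 29 + 1)/19 = 27.5 to (18 × 29 + 3)/21 = 25.0 days. The ratio of reported to emergent incidence is 1.06 to 1.17, against 1.33 to 2.00 above.

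**When onsets are spread out.** With 2 baseline positives and emergent cases on Days 29, 29 and 85, mean onset is 145/5 = 29 days as written and 143/3 = 47.7 days for the emergent cases. The median is 29 in both, so the distortion depends on the statistic chosen.

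**Chance that it arises at all**, 1 − (1 − b)^n for an assumed baseline positivity b:

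| b | n = 12 (largest Part 1 cohort) | n = 30 |
|---|---|---|
| 2% | 21.5% | 45.5% |
| 5% | 46.0% | 78.5% |
| 10% | 71.8% | 95.8% |

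**Whether another provision supplies the rule.** SAP Appendix 5 uses baseline log titer as a covariate in the geometric mean titer models, which does not classify a participant as an ADA responder. The screening, confirmation and titer tiers in Protocol 7.5 classify a sample, not its relation to dosing. Neither closes the gap.

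**The case against.** Several points on the other side have force.

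- **The SAP never says that a pre-dose positive counts.** A reader might infer that it instructs pre-existing antibody to be reported as a response. It does not; the result follows from unrestricted wording. A redacted block comes directly after the formulas and could hold a baseline rule. Still, the legible formulas are complete in themselves, and Protocol 9.6.3 has no such rule.
- **The SAP was written for Part 1.** It supplements the protocol of 16 March 2018 and leaves Part 2 detail to a later amendment. One might conclude that the Part 2 endpoint fails to measure a response. The documents do not go that far: for Part 2 the percentage positive lacks a baseline rule, but onset and duration have no formula at all, so they are undefined rather than wrongly defined.
- **Prior treatment does not show that baseline positivity is likely.** Part 2 inclusion criterion 1b reads "Prior treatment must have included an anti-PD-1/PD-L1 and a platinum-based chemotherapy", which invites that inference for sasanlimab. No document says that antibody raised by another product would test positive in this assay. The argument gives nothing for tremelimumab in Part 2, where criterion 1g bars prior immunologic therapy other than anti-PD-1/PD-L1.
- **The denominator is pre-specified.** If 1, 3 or 5 of 30 participants had no post-dose sample, 3 cases would read 10.0% instead of 3/29 = 10.3%, 3/27 = 11.1% or 3/25 = 12.0%. This is minor and runs opposite to the main effect.
- **The problem is visible and recoverable.** An onset of 1 day identifies a baseline positive, and the data can be reclassified later. That is true, but it leaves the classification to be chosen after the results are known.

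**Conclusion.** The point holds for the text as written. SAP 8.2.1.2 gives explicit onset and duration formulas that return a wrong answer for anyone positive before dosing, and the percentage positive in both documents carries no legible baseline condition. The 1-day onset and the 85-day against 57-day duration follow directly from the formulas and need no assumed rates.

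The effect on summary figures is not known, because the documents give no baseline positivity and no ADA rate in participants. The 13.3% to 20.0% against 10.0%, and 22 to 15 days against 29, rest on chosen counts. The relative effect shrinks as emergent ADA becomes more common, and there is none if nobody is positive at baseline.

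The endpoint is secondary and descriptive. No hypothesis test, sample size, error rate or dose decision depends on it. This is a definition worth correcting before reporting, not a threat to the trial's main conclusions.

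**What to change.** Amend SAP 8.2.1.2 and Protocol 9.6.3, and carry the same definitions into the SAP when it is updated for Part 2:

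1. Define baseline ADA and neutralizing antibody status from the pre-dose Day 1 sample, separately for tremelimumab and sasanlimab.
2. Report three groups separately: baseline-positive; treatment-induced (baseline negative, at least one post-dose positive); and treatment-boosted (baseline positive, with a post-dose titer rise of at least a stated fold). The documents give no fold, so it must be pre-specified from the assay validation.
3. Compute onset and duration only in treatment-induced or boosted cases and only from post-dose samples. Onset is dated at the first sample that meets the induced or boosted definition, and duration starts from that same sample.
4. State how a participant with a missing baseline sample is classified.
5. Optionally, report incidence among participants with at least one post-dose ADA result beside the pre-specified dosed denominator.

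The cost is wording and some programming. The Day 1 sample and titer testing are already planned, so no visit, blood draw or participant is added. The optional denominator would be somewhat smaller.

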8.3. Safety Analysis

A set of summary tables split by treatment will be produced to evaluate any potential risk associated with the safety and toleration of administering PF-06936308.

No formal analyses are planned for safety data. The safety and other endpoints detailed in [Section 6.1](#) will be listed and summarized in accordance with sponsor reporting standards, where the resulting data presentations will consist of subjects from the safety analysis set.

8.3.1. Treatment and Disposition of Subjects

Subject evaluation groups will show end of study subject disposition and will show which subjects were analyzed for pharmacokinetics, as well as for safety (adverse events and laboratory data). Frequency counts will be supplied for subject discontinuation(s) by treatment.

Data will be reported in accordance with the sponsor reporting standards.

8.3.2. Demographic and Clinical Examination Data

A breakdown of demographic data will be provided for age, race, ethnicity, weight, body mass index and height. Each will be summarized by sex at birth and 'All Subjects' for each cohort separately and overall in accordance with the sponsor reporting standards.

8.3.3. Discontinuation(s)

Subject discontinuations, temporary discontinuations or dose reductions due to adverse events will be detailed and summarized by treatment.

Data will be reported in accordance with the sponsor reporting standards.

8.3.4. Adverse Events

Adverse events will be reported in accordance with the sponsor reporting standards.

8.3.5. Laboratory Data

Laboratory data will be listed and summarized by treatment in accordance with the sponsor reporting standards. Baseline is as defined in Section 6.1.3.

8.3.6. Vital Signs Data

Absolute values and changes from baseline for systolic and diastolic blood pressure and pulse rate will be summarized by cohort, treatment and time postdose, according to sponsor reporting standards. Tables will be paged by parameter. Baseline is as defined in [Section 6.2.4](#).

Mean changes from baseline for systolic and diastolic blood pressure and pulse rate will be plotted against time postdose. On each plot there will be 1 line for each treatment. Data from all cohorts will be plotted on the same figure using separate lines. Corresponding individual plots of changes from baseline will also be produced for each cohort and treatment. Maximum absolute values and changes from baseline for vital signs will also be summarized.

8.3.7. ECG Data

Centrally read ECG will be collected. Absolute values and changes from baseline in QT, heart rate, QTcF, PR and QRS will be summarized by cohort, treatment and time postdose using sponsor reporting standards. Tables will be paged by parameter. Baseline is as defined in [Section 6.2.5](#).

Mean changes from baseline in QT, heart rate and QTcF will be plotted against time postdose. On each plot there will be 1 line for each treatment. Data from all cohorts will be plotted on the same figure. Corresponding individual plots of changes from baseline will also be produced for each cohort and treatment.

Changes from baseline in QTcF will also be plotted separately against drug concentrations. This will be a scatter plot for all observations where QTcF and drug concentration are recorded. Different symbols will be used for each treatment. There will be 1 plot for each cohort.

Maximum increase from baseline for QTcF, heart rate, QT, PR and QRS will be summarized by cohort and treatment, according to sponsor reporting standards.

In addition for QTcF, heart rate and QT, the differences between each dose for each subject will be summarized and plotted (N, mean, 90% confidence interval) for each cohort, dose and timepoint (including baseline).

ECG endpoints and changes from baseline (QTcF, PR and QRS) will also be summarized. All values meeting the criteria of potential clinical concern will be listed.

Listings of subjects with any single postdose value ≥ 500 msec will also be produced for QTcF.

QTcB will be listed only and not summarized.

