5.1. Allocation to Treatment

Eligible participants will be enrolled to receive components of VBIR-2 in an open-labeled, unblinded manner. In Part 1, participants will be successively assigned to the next available treatment slot at a dose level decided on after the previous cohort's safety evaluation and ongoing observations of earlier enrolled participants.

Dose level allocation will be performed by the sponsor after participants have given their written informed consent and have completed the necessary baseline assessments. The site staff will email a completed Registration Form to the designated sponsor study team member. The sponsor will assign a participant identification number documenting participant enrollment.

No participant shall receive investigational product until the investigator or designee has received the following information in writing from the sponsor:

- Confirmation of the participant's enrollment;
- Specification of the dose level for that participant;
- Permission to proceed with dosing the participant.

The sponsor or designee will notify the other sites of the inclusion of a new participant, and will inform study sites about the next possible enrollment date.

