9.5.3. ECG

The analysis of ECG results will be based on participants in the safety analysis set with baseline and on-treatment ECG data. Baseline is defined as the pre-dose ECG collected before the first dose of any component of the study treatment.

ECG measurements (an average of the triplicate measurements) will be used for the statistical analysis and all data presentations. Any data obtained from ECGs repeated for safety reasons after the nominal time-points will not be averaged along with the preceding triplicates. Interval measurements from repeated ECGs will be included in the outlier analysis (categorical analysis) as individual values obtained at unscheduled time points.

QT intervals will be corrected for heart rate (QTc) using standard correction factors (ie, Frederica's). Data will be summarized and listed for QT, HR, PR interval, QRS, and QTcF by cohort. Individual QT intervals will be listed by time and cohort. Descriptive statistics (n, mean, median, standard deviation, minimum, and maximum) will be used to summarize the absolute corrected QT interval and changes from baseline in corrected QT after treatment by cohort and time point. For each participant and by treatment, the maximum change from baseline will be calculated as well as the maximum post-baseline interval across time-points. Categorical analysis will be conducted for the maximum change from baseline in corrected QT and the maximum post-baseline QT interval.

Shift tables will be provided for baseline versus worst on treatment corrected QT using Maximum CTC AE Grade. Shift tables will also be provided for ECG abnormality at baseline versus on treatment (yes, no, not done: (n, %)). Participants experiencing clinically -relevant morphological ECG changes will be summarized (including frequency and percentage).

If applicable, the effect of relevant drug concentrations on corrected QT change from baseline will be explored graphically. Additional concentration -corrected QT analyses may be performed. Data may be pooled with other study results and/or explored further with PK/PD models.

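### SAP 8.3.7 puts its only QTcF confidence interval on within-participant differences between doses, a quantity this parallel-cohort design does not properly define

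*SAP*

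**What the plan says.** After listing its main ECG summaries, SAP 8.3.7 adds that, for QTcF, heart rate and QT, "the differences between each dose for each subject will be summarized and plotted (N, mean, 90% confidence interval", and that this is done "for each cohort, dose and timepoint (including baseline". The SAP does not say whether a dose here is a dose level or an administration.

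The same section separately plans change-from-baseline summaries: "Absolute values and changes from baseline in QT, heart rate, QTcF, PR and QRS will be summarized by cohort, treatment and time postdose". It also states: "Maximum increase from baseline for QTcF, heart rate, QT, PR and QRS will be summarized by cohort and treatment". Neither sentence names an interval. Protocol 9.5.3 asks for "changes from baseline in corrected QT after treatment by cohort and time point", and its list of statistics has no interval either: "Descriptive statistics (n, mean, median, standard deviation, minimum, and maximum) will be used to summarize the absolute corrected QT interval". The only other confidence intervals in the SAP are the 80% intervals for antibody titers in Appendix 5.

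On design, Protocol 5.1 says of Part 1: "participants will be successively assigned to the next available treatment slot at a dose level decided on" after review of the previous cohort's safety. SAP 6.2.5 defines a single ECG baseline, taken before the first dose of any component.

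**The concern.** A difference between doses within one participant, tabulated at matched timepoints that include baseline, is a crossover quantity. It needs each participant to receive several doses, each with its own baseline. Here the cohorts are separate, each participant has one assigned level, and there is one baseline, so a between-dose difference at baseline cannot be formed. The wording may come from a template for another design. The SAP also refers to randomization (5.6.1, 5.6.2), washout (6.2.2) and a placebo group (Appendix 5), none of which this open-label escalation has. That origin is a supposition; the mismatch is not.

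At stake is what the displayed interval would mean. A programmer would have to choose a definition of dose, possibly with the data in view. The result could be an empty table, an interval from a few dose-reduced participants, or an interval near zero that a reader takes as reassurance about QTcF.

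**Working it through.** The documents give no QTcF effect, QTcF SD or dose-reduction rate, so there is no planned figure to reproduce. Assumed values are marked as such.

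**Reading 1: dose means dose level.** A participant contributes only if the level changed.

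- Protocol 5.4.5.1 and 5.4.5.2 rule out re-escalation of AdC68 and tremelimumab. Section 5.4.5.3 describes reductions of sasanlimab, or leaving it out for one dose.
- One trigger is the outcome itself: under Protocol 7.1.5 and SAP 6.2.5, a QTcF hold is followed by restart at a lower level.
- In the first cohort (AdC68 2×10^11 VP with 5 mg pDNA) no lower level is tabulated for either component, so N would be zero.

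For the other cohorts, let each participant be reduced independently with assumed probability p. An interval needs at least two contributors:

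P(at least 2) = 1 − (1−p)^n − n·p·(1−p)^(n−1)

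For example, with n = 4 and p = 0.10: 1 − 0.6561 − 0.2916 = 0.052.

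| n | p = 0.10 | p = 0.20 | p = 0.30 |
|---|---|---|---|
| 4 | 0.052 | 0.181 | 0.348 |
| 6 | 0.114 | 0.345 | 0.580 |
| 12 | 0.341 | 0.725 | 0.915 |

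SAP 2.1.2 plans 2 to 4 DLT-evaluable patients per cohort and up to 12 on expansion. Protocol 3.1 reports 36 participants in six cohorts, an average of 6. At n = 4, 65% to 95% of cohorts would have no interval; at n = 6, 42% to 89%. With exactly two contributors the 90% half-width is 6.31·SD/√2, about 4.5 SDs.

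Contributors would also show only part of any effect. If it were linear in dose (assumed), a change from 80 to 40 mg tremelimumab would show (80−40)/80 = 50% of it, and from 300 to 130 mg sasanlimab (300−130)/300 = 57%.

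**Reading 2: dose means administration.** Write QTcF at visit j as participant level + d_j + error, with d = 0 at the pre-dose baseline. The expected difference between visits k and j is d_k − d_j. Take an illustrative prolongation of 10 ms:

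- Both visits on treatment, constant effect: 10 − 10 = 0 ms. The effect cancels.
- Both on treatment, effect 1.5 times as large at the later visit (assumed): 15 − 10 = 5 ms. It cancels in part.
- Earlier visit is the Day 1 ECG. Footnote 22 of the Part 1 schedule puts dosing after the day's other assessments, so this ECG is the baseline: 10 − 0 = 10 ms. The difference is change from baseline.

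AdC68 is given on Day 1 of each cycle and pDNA on Days 29, 57 and 85, so an effect belonging to one of them would not fully cancel either.

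**The interval after the fix.** The half-width for mean change from baseline is t(0.95, n−1)·SD/√n. At n = 4 and SD 8 ms: 2.353 × 8/2 = 9.4 ms.

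| n | SD of change 8 ms | 12 ms | 16 ms |
|---|---|---|---|
| 4 | 9.4 | 14.1 | 18.8 |
| 6 | 6.6 | 9.9 | 13.2 |
| 12 | 4.1 | 6.2 | 8.3 |

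The SDs are assumed.

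**The case against.** The disputed sentence is an addition to a fuller set of analyses. For all participants with usable ECGs, 8.3.7 summarises change from baseline, plots means and individuals, summarises the maximum increase, plots change against concentration, and lists QTcF values of 500 msec or more. Protocol 9.5.3 adds n, mean and SD of the change, from which an interval can be derived, plus categorical and shift tables. SAP 8.3 plans no formal safety analyses. The sponsor reporting standards cited in 8.3.7 are not supplied and might contain further intervals. In cohorts of four, the corrected interval would itself be wide.

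All of this stands, and it limits the point to one display. Two further objections also hold. Dose reduction need not reflect a participant's own toxicity, because SAP 2.1.5 allows a reduction for all ongoing patients. And under the administration reading, pairs that include the Day 1 ECG are sound.

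What does not follow is that the sentence can stay as it is. The Day 1 pairs duplicate the change-from-baseline summary, while the remaining pairs compare on-treatment visits. A wide interval on the right quantity shows honestly how little a small cohort can establish.

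**Conclusion.** The only QTcF interval specified in the documents sits on a quantity that the design does not properly define. Read as dose level, it is empty or rests on the few participants whose level changed, some of them possibly because of QTcF. Read as on-treatment administrations, it removes a constant effect. The design mismatch rests on the text alone; the contributor probabilities rest on assumed, independent reduction rates of 10% to 30%, and the cancellation on an effect that is constant across visits.

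Three stronger inferences are not supported:

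- That QTcF prolongation goes unestimated, or is estimated only in dose-reduced participants. Change from baseline is summarised and plotted by cohort.
- That the interval would centre on zero whatever the drug does. Accumulating or component-specific effects, and differences against Day 1, contradict that.
- That a trial decision depends on this interval. No rule uses it.

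No detection rates are given. They would need an SD and a constant effect that the documents do not supply, and under a constant effect they would only return the tail error of a 90% interval. SAP section 2 describes the SAP as both supplementing and superseding the protocol's statistical text. Nothing in the protocol is displaced here, but nothing there supplies the missing interval.

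**What to change.** In SAP 8.3.7, replace the sentence on between-dose differences with: 'Mean change from pre-dose baseline in QTcF, heart rate and QT, with N and two-sided 90% confidence interval, for each cohort and nominal time point.' Remove the within-participant between-dose differences, or keep them only as a listing for participants whose dose level changed.

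The cost is SAP wording, one added column in a planned table and error bars on planned plots. No new ECGs or other data are needed.
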